6 DESCRIPTIVE ANALYSES

6.1 Participant flow

For the co-primary outcomes, both cluster and participant throughput will be summarised in CONSORT diagrams specific to the outcome of interest. The four main CONSORT diagrams are (a) directly assessed outcomes (cross-sectional), (b) directly assessed outcomes (cohort), (c) indirectly assessed outcomes (cross-sectional) and (d) indirectly assessed outcomes (cohort).

6.2 Representativeness of sample

N/A

6.3 Baseline comparability of randomised groups

To assess the adequacy of our randomisation process in achieving balanced groups we will compare the characteristics of RNHs (location, type and size of home) and individuals (age, sex, baseline assessment scores) in our intervention and control arms using simple descriptive statistics without recourse to hypothesis testing.

6.3.1 Demographics

Age, sex, ethnicity, age at which left school (proxy for social class) and length of residence in home will be checked descriptively.

6.3.2 Prior and concurrent medications

On antidepressants (yes/no)

6.3.3 Baseline and screening conditions

GDS-15, EQ-5D (self-report and proxy), MMSE, Barthel Index, fear of falling, current pain

6.3.4 Baseline medical history

Terminal or other serious illness are exclusion criteria

6.3.5 Baseline physical exam

Consented/assented residents were given a physical assessment (SPPB)

6.3.6 Cluster characteristics

Type (a combination of ownership and services), and size (number of beds) of RNH Number of beds and occupancy (see table 2)

6.3.7 Characteristics of care providers where applicable

Type of RNH: local authority/voluntary/private & care/private & nursing/dementia specialist

6.4 Comparison of losses to follow-up

Proportion followed up at 6 months and at 12 months in each arm with detail presented on reasons for loss to follow-up presented in CONSORT diagrams.

6.5 Comparison of compliance to treatment and protocol

Not applicable

6.6 Emergency or accidental unblinding of randomised treatment

Not applicable

7 INTERIM ANALYSES AND SAFETY MONITORING ANALYSES

7.1 Purpose of interim analyses

To assess original sample size for adequacy.

7.2 Monitoring plan

None

7.3 Stopping rules

None

7.4 Measures taken to minimise bias

N/A

7.5 Adjustment for p-values

N/A

7.6 Interim analysis for sample size adjustment

Using data from recruitment up to November 2009, baseline data was analysed to reestimate the power of the study. The intracluster correlation coefficient (ICC) of GDS-15 at baseline was estimated (pooled across Warwick and London). Mean cluster size was ascertained and the sample size rechecked for adequacy. See tables 3 and 4 for details.

8 ANALYSIS OF CO-PRIMARY OUTCOMES

8.1 Definition of outcome measures

- Difference in proportion of residents depressed (defined in 2.2.1.) at 12 months between intervention and control homes.
- Change in number of depressive symptoms at 6 months in all those who were considered depressed at baseline, according to their GDS-15 score.
- Change in number of depressive symptoms at 12 months in all those who were present at baseline.

8.2 Descriptive statistics for outcome measure

By study arm, count and percentage of all participating residents depressed at 12 months, of residents present and depressed at baseline and at 12 months, and of residents present and depressed at baseline and at 6 months.

8.3 Primary analysis

To assess the difference in proportions depressed at 12 months between intervention and control homes we will use mixed effects modelling (with a random effect to account for clustering by RNH) with a binomial family and a logit link function (to handle the binary outcome) in Stata (xtmelogit command).

To assess the change in severity of depressive symptoms at 6 and 12 months between intervention and control homes we will use mixed effects modelling (with a random effect to account for clustering by RNH) with a Gaussian family and the identity link function in Stata (xtmixed command).

Each model will include the baseline measure of the outcome (except for MMSE), as well as the minimisation variables home type, home size and the stratification variable location. In addition, we will include individual baseline SPPB score and whether or not the resident was on antidepressants (cohort analyses only). We will also include, at the home level, the proportion of residents with moderate to severe cognitive impairment at baseline (i.e. with an MMSE<20).

We will examine the correlations between the covariates to assess any potential multicollinearity problem. This will be done by fitting a linear regression model and requesting the variance inflation factors (VIFs). A VIF>10 indicates severe multicollinearity. VIFs between 5 and 10 indicate some problem.

For the outcomes which indicate a change in severity of depression for those depressed at baseline, we will use a similar strategy, but measurements at baseline and outcome will be on the same individual. We will therefore introduce baseline levels of depression severity as a covariate at the individual level.

All covariates listed in section 5.9 will be entered into the model at the same time and none will be removed unless there is evidence of multicollinearity, in which case, the collinear covariate providing the best fit will be retained.

The regression coefficient for continuous outcomes, odds ratio for binary outcomes, proportional odds ratio for ordered outcomes and incidence rate ratio for rate outcomes, of the treatment (intervention vs. control) variable, and its 95% confidence interval, will be reported along with the p-value.

8.4 Assumption checks

Appropriate model diagnostics will be checked: e.g. normality (continuous outcomes only) and homoscedasticity of residuals and normality of random effects.

8.5 Other analysis supporting the primary (inc. sensitivity analyses)

Residents joining post-randomisation

There are two groups of residents to consider here. By far the largest group is new residents who join the study at 3, 6 or 9 months post-randomisation. The second group comprises a small number of residents who were present in the home at baseline and for whom some data were collected soon after their home was randomised. For example, proxy EQ-5D just before randomisation and a self-completed one just after randomisation.

In the cross-sectional analysis inclusion criteria will be based on length of time resident in home; thus individuals from these two groups may be included in the main analysis. A sensitivity analysis will exclude these individuals.

In the cohort analyses these two groups will not be included in the main analysis. They will be included in a sensitivity analysis providing that they have been resident in the home prior to pre-determined cut-offs set at about 3 months prior to each outcome end point. Their baseline will be the earliest time point at which they are assessed. The cohort analysis has endpoints at 6 and 12 months. This will provide an analysis population that is comparable to that in the health economics analysis.

Barts and The London School of Medicine and Dentistry

Pragmatic Clinical Trials Unit

Missing values

For cohort study outcomes:

Assuming that the linear predictor is correct, the mixed models will provide efficient and unbiased effect estimates despite missing values in covariates, assuming that the missingness mechanism is missing at random (MAR).

After the analyses set out in this plan have been carried out, [name] will perform analyses under various missing data assumptions, to be detailed in a separate analysis plan.

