1.4 Changes from planned analysis in the protocol

We will use mixed models rather than generalised estimating equations (GEEs) for the analysis. One motivation for this is the less strict assumption about missing data made (i.e. data missing at random rather than missing completely at random).

One of the co-primary outcomes was changed to a secondary outcome with approval of the TSC [See TSC minutes from 22/09/2009]. Following an early decision [See TMG minutes from 01/04/2009] partway through the trial to exclude dementia homes, only one dementia home was included.

There was therefore only one dementia-specialist home in the study, and though strictly speaking, dementia-specialist status was included in the minimisation algorithm, it effectively had no influence in the randomisation schedule (as there was no adjustment done on "dementia specialist" status homes between the two arms). As such, we need not adjust for it.

Exclusion criteria for homes were also modified from protocol (minutes 11/02/2009) though this should not affect planned analyses.

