5.5 Methods for withdrawals, loss to follow-up and missing data

Numbers lost to follow up and withdrawal from the study will be described by arm to try and establish if there is difference in attrition rates.

Cross-sectional: N/A

Cohort analyses: as all cohort analyses will be modelled using maximum likelihood methods, outcomes will not be imputed as we do not, at this stage, wish to assume that measurements are missing at random (MAR).

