12 AMENDMENTS TO VERSION 1.0

Barthel Index replaced by SPPB as a measure of physical function because Barthel Index was missing for all residents in one home at baseline.

If one or two items are missing in the Social Engagement Scale, the score will be pro-rated according to the rule written in 5.14.

To avoid having a category with only one member, local authority homes and voluntary homes will be collapsed into one category for the purpose fitting the 'home type' design variable in the analysis.

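### Section 8.5 says the mixed models cope with missing covariates, but the models named drop those residents; section 5.5 disclaims the missing-at-random assumption that 1.4 and 8.5 rely on

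*SAP*

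**What the plan says.** - **Section 8.5 (Missing values, cohort outcomes):** "the mixed models will provide efficient and unbiased effect estimates despite missing values in covariates". The sentence is conditional on a correct linear predictor and on MAR.
- **Section 8.3:** the continuous co-primary outcomes are fitted "with a Gaussian family and the identity link function in Stata (xtmixed command") and the binary one "with a binomial family and a logit link function (to handle the binary outcome) in Stata (xtmelogit command"), each with a random effect for home. All section 5.9 covariates go in together, and only multicollinearity can remove one.
- **Section 5.9:** the individual-level covariates are age, sex, SPPB and antidepressant use, plus the resident's own baseline outcome in cohort analyses.
- **Section 5.2.2:** the available-case set depends on having a valid outcome and, for cohort analyses, a valid pre-randomisation value of it. Other covariates are not mentioned.
- **Section 5.5 (cohort analyses):** "outcomes will not be imputed as we do not, at this stage, wish to assume that measurements are missing at random (MAR"). The same sentence relies on maximum likelihood. The cross-sectional entry reads N/A.
- **Section 1.4:** mixed models are preferred to GEE partly for their weaker assumption, "data missing at random rather than missing completely at random".
- **Section 8.5, closing sentence:** a named analyst "will perform analyses under various missing data assumptions, to be detailed in a separate analysis plan".

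**The concern.** MAR protects a likelihood analysis against missing values of the variables that the likelihood models. Here that is the outcome alone. The covariates are conditioned on and given no distribution, so a record with a missing covariate contributes nothing. Residents with a valid GDS-15 at both times can therefore be lost because a nuisance covariate is absent. The set fitted will then be smaller than the set defined in 5.2.2, and no rule in the plan prevents this.

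The second problem is that a reader cannot tell which assumption the co-primary results rest on. Declining to impute does not avoid MAR. With one endpoint per model, analysing the observed outcomes still requires missing outcomes to be ignorable given the covariates and arm.

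At stake are precision, the population to which the estimate applies, and a correct statement of the assumption behind it.

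**Working it through.** **1. The passages side by side.** Sections 1.4 and 8.5 rest on MAR; 5.5 says it is not to be assumed. Section 8.5 says missing covariates do no harm; 8.3 names commands that delete such records and forces every covariate in. Section 5.2.2 defines a set that ignores covariate completeness. No section says what to do when a covariate is missing.

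**2. Reproducing Table 4.** Inputs: difference 1.2; SD 3.12 (12-month GDS-15) or 2.21 (6-month, depressed at baseline); ICC 0.053; mean cluster size at follow-up 7.5 or 3.9; 80% power; two-sided 5% (section 5); allocation 2:3 (section 3.1).

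Simple N = (1.960 + 0.842)² × SD² × (1/0.6 + 1/0.4) / 1.2². After rounding up by arm this gives 222 for 12 months (stated 224) and 112 for 6 months (stated 112).

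Design effect = 1 + (m − 1) × 0.053.
- 12 months: 1 + 6.5 × 0.053 = 1.3445; 224 × 1.3445 = 301.2 (stated 301).
- 6 months: 1 + 2.9 × 0.053 = 1.1537; 112 × 1.1537 = 129.2 (stated 130).

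The table's figures hold, so they can carry the next step.

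**3. Cost in precision, 12-month GDS-15.** The share of residents lacking a covariate is not given, so a range is assumed. With the number of homes fixed, variance is proportional to [1 + (m − 1) × 0.053] / m. The last two columns use 78 homes.

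| Assumed share dropped | m | Variance factor | SE ratio | Residents analysed | Power |
|---|---|---|---|---|---|
| 0% | 7.5 | 0.1793 | 1.00 | 585 | 0.98 |
| 5% | 7.125 | 0.1859 | 1.02 | 556 | 0.97 |
| 15% | 6.375 | 0.2015 | 1.06 | 497 | 0.96 |
| 25% | 5.625 | 0.2214 | 1.11 | 439 | 0.94 |

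Power with nobody dropped: 585 / 1.3445 = 435.1 effective residents; SE = 3.12 × √(1/(0.6 × 435.1) + 1/(0.4 × 435.1)) = 0.305; 1.2 / 0.305 = 3.93; power = Φ(3.93 − 1.96) = 0.98. With 25% dropped: 438.75 / 1.2451 = 352.4; SE = 0.339; ratio 3.54; power 0.94.

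For 6-month GDS-15 in those depressed at baseline, 78 × 3.9 = 304 residents falls to 228 at 25%, and power goes from 0.99 to 0.97.

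**4. Bias.** A random-intercept linear model was simulated with 78 homes of 8 and a true effect of −1.2, under assumed missingness mechanisms.

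| Covariate missingness | Complete-case mean | SD, complete case vs full data |
|---|---|---|
| Completely at random, 20% | −1.20 | 0.273 vs 0.258 |
| Depends on baseline score and arm | −1.21 | 0.283 vs 0.259 |
| Depends on unmeasured frailty that also drives outcome, not on arm, about 22% | −1.19 (full data −1.19) | 0.29 vs 0.27 |
| Depends on the observed outcome, both arms | −1.11 | 0.260 vs 0.249 |
| Depends on the observed outcome, one arm only | −1.47 | 0.261 vs 0.251 |

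The first three rows show lost efficiency without bias. The last two are also MAR, so MAR alone does not deliver what 8.5 claims. They do require missingness of the covariate to follow the outcome.

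**The case against.** The strongest defence is that a reader who infers a biased treatment comparison goes too far. The sentence in 8.5 concerns cohort outcomes. Section 3.4 says their baseline assessments were made blind to allocation, 5.2.2 requires the baseline outcome before randomisation, and 8.5 keeps late baseline data out of the main cohort analysis. Missing SPPB or antidepressant status in that group can hardly depend on arm or on a treatment-affected outcome. The two biased rows above are therefore not a credible description of it. This stands for the cohort analyses. It does not extend to residents who joined after randomisation and enter the cross-sectional analysis, because 3.4 says staff then knew the allocation.

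Further limits also stand:

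- **Power.** Starting from the minimum numbers in Table 4 (301 and 130), 20% deletion gives power of about 0.74 and 0.73. With 78 homes randomised, those minimums are well below the numbers expected, so this is not the trial's likely position.
- **Reach.** Not every model carries individual SPPB. It is omitted where SPPB is the outcome, the fracture row of Table 5 uses a home-level aggregate, and a bracket in 8.3 leaves its place in cross-sectional models unclear.
- **Barthel.** Section 12 records that "Barthel Index was missing for all residents in one home at baseline" and that SPPB replaced it. This shows the team dealing with one missing covariate. It does not show that SPPB is often missing, or missing in the frailest.
- **Sensitivity analyses.** One might infer that they will be designed once results are known. Section 8.5 says only that they are performed afterwards under a separate plan, which is not at hand.
- **Single-endpoint models.** These are standard. Section 9.3 even allows a repeated-measures MMSE model, though that too would drop rows with missing covariates.

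None of this rescues the covariate claim or removes the conflict with 5.5.

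**Conclusion.** The covariate statement in 8.5 is wrong for the models named, and 5.5 contradicts 1.4 and 8.5 on MAR. The sure consequence is lost precision and an analysed population narrower than 5.2.2 defines. If the effect differs in the residents dropped, the estimate also refers to a different group. Bias in the cohort comparison would need missingness that depends on the outcome beyond the modelled covariates and arm, and nothing in the plan points to that.

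The size is modest: a standard error about 2% to 11% larger for 12-month GDS-15, and at worst power of about 0.94 instead of 0.98. These figures rest on assumed missingness of 5% to 25%, spread evenly over homes, and on Table 4's ICC, unadjusted SD and anticipated cluster size, not on achieved numbers. The trial is not threatened. The statements should still be corrected before analysis, because they govern two of the three co-primary outcomes and no rule for missing covariates exists for any of them.

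**What to change.** 1. In 8.5, delete the covariate claim or replace it with a statement that these models omit residents with a missing covariate unless it is imputed.
2. Reconcile 5.5 with 1.4 and 8.5: state that the primary models assume outcomes are MAR given the covariates and arm.
3. Keep every resident with a valid outcome (and a valid baseline outcome in cohort analyses). Impute missing baseline covariates with the mean or a missing indicator, using neither arm nor outcome. Apply this to the cohort models and to any cross-sectional model that carries individual covariates, replacing the N/A in 5.5.
4. Report by arm how many residents had a covariate imputed.

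The cost is a few sentences, a few lines of code and a little more analysis work. Modelling 6- and 12-month GDS-15 jointly is an option, not part of the correction.

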9 ANALYSIS OF SECONDARY OUTCOMES

9.1 Definition of outcome measures

- The proportion of depressed residents, with 'depression' measured prior to randomisation, that experience remission from their 'depression' six months after their home was randomised.
- . Cognitive function: Mini Mental State Examination as a continuous variable
- EQ-5D as a continuous variable: proxy and self-reported
- . Mobility: Short Physical Performance Battery (SPPB) as a continuous variable.
- Falls:
 - (a) Binary fear of falling: "Are you afraid of falling" yes/no response from participants.
 - (b) Rate of peripheral fractures as a marker for injurious falls. We will identify these from the RNH (home aggregate level) and hospital records (individual level).
- Pain: ordinal 5-point rating scale at each follow-up.
- The Social Engagement Scale uses six items from the Minimum Data Set residential assessment instrument (MDS-RAI).
- Medication use: For antidepressants, other psychoactive drugs, analgesics and NSAIDs we will convert these into the number of defined daily doses (DDD) used over one year (http://www.whocc.no).
- Hospital admissions: cause and duration of any hospital admissions during the study period from participants' hospital records. We will code these admissions into Diagnosis Related Groups to identify any peripheral fractures.

9.2 Descriptive statistics for outcome measure

Continuous outcome: n, mean, SD, median, 10th and 90th centiles, by arm. Dichotomous outcome: n (%), by arm.

9.3 Secondary analysis

The analysis strategy is the same as for the co-primary outcomes.

- Remission of depression: reduction in proportion of participants depressed in the intervention arm. A mixed effects logistic model will be defined. This will be fitted using the xtmelogit command.
- Cognitive function Mini Mental State: We will compare the rate of change in MMSE cluster mean at baseline and at end of intervention in exercise and control homes.
 We could construct linear mixed effects models with MMSE at 0, 6, and 12 months, with random effects for RNH. This will be fitted using the xtmixed command.
- EQ-5D: we will use linear mixed models, with RNH as a random effect. This will be fitted using the xtmixed command.
- Mobility: (SPPB) we will use linear mixed models, with RNH as a random effect.
 This will be fitted using the xtmixed command.
- Falls

Binary fear of falling: reduction in proportion of participants declaring fear of falling in the intervention arm. A mixed effects logistic model will be defined. This will be fitted using the *xtmelogit* command.

- Pain: 5-point scale. Ordinal mixed effects logistic regression (either in Stata using the gllamm command or in MLWiN.)
- The Social Engagement Scale uses six items from the Minimum Data Set residential assessment instrument (MDS-RAI). Ordinal mixed effects logistic regression (either in Stata using the *gllamm* command or in MLWiN.)

The following outcomes will not be modelled. However, medication use and hospital admissions are important for the health economic analysis (see separate analysis plan).

- Medication use (descriptive statistics only)
- · Hospital admissions (descriptive statistics only)
- All-cause mortality.

9.4 Assumption checks

Appropriate model diagnostics will be checked: normality (continuous outcomes) and homoscedasticity of residuals, normality of random effects.

9.5 Other analysis supporting the secondary (inc. sensitivity analyses)

See section 8.5 for details.

10 SAFETY AND TOLERABILITY ANALYSES

10.1 Drug exposure

N/A

10.2 Adverse events

Data on adverse events was not collected.

10.3 All adverse events

N/A

10.4 Adverse events leading to withdrawal

N/A

10.5 Serious adverse events

According to the 'adverse event reporting protocol', an SAE is any untoward or medical occurrence that: results in death or is life threatening or requires hospitalisation or results in persistent disability of incapacity or requires medical intervention to prevent one of these (or is otherwise considered medically significant by the investigator).

SAEs can be classified as directly attributable (i.e. occur during a study assessment or getting to or from or occur during a group-activity session), or indirectly attributable (i.e. at any other time between randomisation and end of follow-up).

Table 6 Classification of anonymised fracture-related deaths, and fractures data.

Deaths* and Fractures (indivdiual level data)	Attribution of SAE			
	direct	indirect		
study participant (intervention)	A, E	otherwise		
non study participant (partaking in exercise)	E	otherwise		
study particpant (control)	Α	otherwise		

A = during study assessment

E = during exercise

otherwise = not (A or E)

Difference in rates of peripheral fractures between intervention and control homes (mixed effects Poisson model with resident-time in study as the exposure variable). This will be fitted using the *xtmepoisson* command.

Reporting of cause of death data

All deaths in residents will be reported and documented. We will have data on deaths amongst all residents from all homes. This will not provide accurate dates of death and characteristics of residents. We will conduct a simple comparison of total death rate in the two trial arms. For those who have consented/assented to have their data used, we will have exact date of death from death certification data, plus age and gender and all the other baseline variables. For this group we will construct Kaplan-Meier plots and carry out log-rank tests to see if there is any difference in all cause mortality over time. We will also consider using Cox's proportional hazards models (streg command) or logistic regression to allow for covariates depending on the number of deaths.

All cause of death data will be based on ICD10 coding provided by MRIS. These deaths data are provided as the underlying cause of death and also as the factors contributing to death.

^{*} fracture-related deaths (ICD10 chapter S)

This is a safety analysis that will be presented for all subjects contributing data to the study.

We will present the number of deaths for which any injury, i.e. any underlying of contributory cause of death includes an ICD10 code that starts with an 'S', has contributed to the cause of death. We will present these as fracture-related deaths per year of exposure. We will estimate difference in fracture related death rate within a 95% confidence interval.

For the primary cause of death outcome the underlying cause of death from the MRIS data will be used. This will presented as number of deaths during study period, subdivided by ICD chapters; i.e. the first character in the ICD code, between each group. No statistical analyses will be presented.

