2.2 Outcome measures

The following table (table 1) details the primary outcome measure (GDS) and various secondary outcome measures, their data types, and at which end-points they apply.

Table 1: outcomes, end-points and data types

1		At 12 months in all	Change at 6 and 12 months	Change at 6 months in those	Remission of depression at 6m	All residents who
	Outcome measure	present at end of study	in all present at baseline	depressed and present at baseline	in those depressed at baseline	provided consent at any time
primary	GDS	dichotomous	continuous (12 months)	continuous		
	GDS	continuous			dichotomous	
	MMSE	continuous	continuous			
	EQ-5D *	continuous	continuous			
secondary	SPPB	continuous	continuous**			
	Pain rating today	ordinal (5 points)	ordinal (5 points)			
	Social engagement	ordinal (6 points)	ordinal (6 points)			
	Fear of falling	dichotomous	dichatamous			
safety	Peripheral fractures					rate
salety	All-cause mortality					rate

^{*} both proxy and self-completed

** at 12 months only

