3.4 Treatment masking (blinding)

All baseline assessments for the cohort comparison were collected blind to treatment allocation. Our primary measure, GDS-15, and other questionnaire data at follow-up were collected by research nurses not blinded to the RNH's allocation status. Our interpretation of cause of death data was blind to allocation.

For new residents joining the study after randomisation allocation concealment was impossible because all RNH staff and study staff visiting the RNHs were aware of the home's allocation. We tried to protect against recruitment bias resulting from lack of allocation concealment by ensuring that we were aware of all new residents and reasons for exclusion from the study were monitored.

We will compare, descriptively or by graphical methods, the GDS-15, MMSE and SPPB scores of residents recruited into the study post randomisation with those recruited pre-randomisation, by arms, for evidence that (a) residents recruited post-randomisation differ between arms and (b) the ratio of participants assenting to those consenting changes over time. We hypothesise that less effort may be made to recruit residents at 9 months than at 6 months, than at 3 months, than pre-baseline. Assent requires more effort to attain than consent and so this ratio may decrease over time.

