4.3 Timing of data collection

Residents, recruited between January 2009 and May 2010, underwent baseline assessments by the recruitment team to establish eligibility and once all had consented/assented/refused, the whole home was randomised to either the exercise intervention or depression awareness training. Follow-up visits were made to all homes at 3, 6, 9 and 12 months post-randomisation. Repeated attempts within one month of the assessment date were made as necessary by the recruitment team to obtain data from participants who were unavailable for assessment at the fixed follow-up points (i.e. at 3, 6, 9 or 12 months). At these fixed follow-up points (except 12 months), residents new to the home since the last visit were invited to participate, baseline assessments were performed and consent/assent was sought. NB this does not include existing study participants who had moved into the home during this time. Furthermore, residents that had previously refused consent/assent could change their mind and become study participants subject to a satisfactory baseline assessment and consent/assent being given.

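### The individual-level mortality comparison in SAP 10.5 pools residents consented before randomisation with residents recruited afterwards by staff who knew the allocation, sets no time origin or delayed entry, and has no analysis restricted to pre-randomisation consenters.

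*SAP*

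**What the plan says.** SAP 10.5 describes two mortality comparisons. One is a simple comparison of total death rates using deaths among all residents of all homes; the section says these data lack accurate dates of death and resident characteristics. The other is at individual level: "For those who have consented/assented to have their data used, we will have exact date of death from death certification data". The method follows: "For this group we will construct Kaplan-Meier plots and carry out log-rank tests to see if there is any difference in all cause mortality". Cox or logistic models will be considered, depending on the number of deaths. On scope, 10.5 adds: "This is a safety analysis that will be presented for all subjects contributing data to the study". Table 1 (2.2) places all-cause mortality in the column for residents who "provided consent at any time".

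Consent continued after randomisation. At the fixed visits before 12 months (4.3), "residents new to the home since the last visit were invited to participate, baseline assessments were performed and consent/assent was sought", and "residents that had previously refused consent/assent could change their mind and become study participants". On masking, 3.4 says: "For new residents joining the study after randomisation allocation concealment was impossible".

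Section 8.5 deals with post-randomisation joiners for the effectiveness outcomes. They are left out of the main cohort analyses, and for the cross-sectional analysis, "A sensitivity analysis will exclude these individuals". Section 9.5 refers back to 8.5 for the secondary outcomes. Section 10.5 has no counterpart.

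**The concern.** Comparing mortality rates between arms is safety objective (b) in 2.1.3. The individual-level analysis is the only one with exact dates and covariates, yet its population is partly formed after randomisation. Two mechanisms follow.

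- **Selection.** Late joiners were recruited with the allocation known. If fitter or frailer residents were recruited more readily in one arm, the arms differ in prognosis for reasons unrelated to the exercise programme. No choice of time origin removes this.
- **Immortal time.** A late joiner must be alive at consent. If follow-up is counted from home randomisation without delayed entry, the time before consent is death-free by construction. For refusers who consented later, the same happens if time runs from home entry.

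Either mechanism could hide a mortality difference or create one. The SAP names the recruitment risk in 3.4 and acts on it for the effectiveness outcomes, but not here.

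**Working it through.** The SAP gives no event count, hazard ratio (HR) or power for mortality, so there is no planned figure to reproduce. The check asks how far each mechanism moves the result when the true HR is 1.

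**Inputs from the SAP.** Annual mortality up to 34% (3.5), allocation 2:3 (3.1), joiners entering at 3, 6 and 9 months (4.3), 12 months of follow-up, two-sided 5% (5).

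**Assumptions not in the SAP.** Exponential deaths; joiners split equally over the three visits; joiners forming 10% to 30% of each arm's participants; selected joiners with 0.5 or 0.7 times the usual hazard; no clustering by home.

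**Step 1, building blocks.**
- Rate: λ = −ln(1 − 0.34) = 0.4155 per year.
- Pre-randomisation resident: 0.34 deaths and 0.34/0.4155 = 0.8183 person-years.
- Joiner, with 0.75, 0.50 or 0.25 years left: mean death probability 0.1847 and 0.1847/0.4155 = 0.4444 person-years at risk. The mean time before entry is 0.5 years.

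**Step 2, immortal time alone.** For joiner share f, true person-time is P = (1 − f)·0.8183 + f·0.4444. Counting from home randomisation without left truncation uses P + 0.5f, so the observed rate is λ·P/(P + 0.5f).
- f = 15%: P = 0.7622; rate = 0.4155 × 0.7622/0.8372 = 0.3783.
- f = 30%: P = 0.7061; rate = 0.4155 × 0.7061/0.8561 = 0.3427.
- 15% intervention against 30% control: 0.3783/0.3427 = 1.10.

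Solving the large-sample Cox score equation with the same inputs agrees to within rounding. The rejection column takes 1000 residents (roughly 300 deaths).

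| Joiner share, intervention / control | HR, no delayed entry | Log-rank rejection | HR, delayed entry |
|---|---|---|---|
| 20% / 20% or 30% / 30% | 1.00 | 5% | 1.00 |
| 25% / 15% | 0.94 | 8.7% | 1.00 |
| 15% / 25% | 1.07 | 8.8% | 1.00 |
| 30% / 15% | 0.91 | 13.6% | 1.00 |
| 15% / 30% | 1.11 | 13.7% | 1.00 |
| 30% / 10% | 0.88 | 20.3% | 1.00 |
| 10% / 30% | 1.14 | 20.7% | 1.00 |

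With equal shares and a true HR of 1.3, the analysis without delayed entry gives 1.29, so almost no bias.

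**Step 3, selection alone, with delayed entry applied.** Take a 30% share in both arms and half the hazard in intervention-home joiners. Their mean death probability falls to 0.0979, with 0.4710 person-years.
- Deaths per resident: 0.7 × 0.34 + 0.3 × 0.0979 = 0.2674.
- Person-years per resident: 0.7 × 0.8183 + 0.3 × 0.4710 = 0.7141.
- Rate 0.2674/0.7141 = 0.3744, and HR = 0.3744/0.4155 = 0.90.

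The same selection in control homes gives 1.11. A milder case (20% share, 0.7 times the hazard) gives 0.96 or 1.04. Running time from each resident's own entry gives the same values.

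**Step 4, restriction.** With only residents consented before randomisation, both mechanisms are absent; simulation gives HR 1.00 and 5.0% rejection.

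**The case against.** Five points can be made for the plan.

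- **Another mortality comparison exists.** A reader might infer that mortality has no analysis free of consent selection. The SAP does not support that. The all-resident death-rate comparison in 10.5, with the safety population and person-time denominator of 5.2.4, does not depend on consent. This stands. However, 10.5 itself says those data lack accurate dates and resident characteristics, and they include people admitted after randomisation.
- **The time origin is open, not wrong.** A reader might infer that the SAP counts joiners' pre-consent time as follow-up. It does not say so. Section 5.2.4 speaks of time in the home, and the fracture model in 10.5 uses time in study. The fault is non-specification. It matters because the choice can move the result and, per 5.1, the study statistician is not blinded.
- **No hazard ratio is firmly planned.** Kaplan-Meier and log-rank yield none, Cox is only to be considered, and 9.3 lists all-cause mortality among outcomes not modelled. The point is therefore about the log-rank result and any Cox model that follows.
- **The sizes rest on assumed imbalance.** No joiner counts are given, and all homes had the same visit schedule. With equal shares and no true effect, the immortal-time part is nil. The assumed biases are also no larger than sampling error: with about 335 deaths split 2:3, the standard error of the log HR is 1/√(335 × 0.24) = 0.11. All true, but the selection part does not need unequal shares.
- **Recruitment bias is recognised.** Section 3.4 monitors exclusions and compares GDS-15, MMSE and SPPB of early and late recruits by arm. That describes selection; it does not correct the mortality test.

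A whole-home intervention is also a fair reason to show everyone exposed, so the wider analysis should stay, beside a restricted one.

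**Conclusion.** The point holds for the individual-level analysis in 10.5. Its population is stated to be all who consented or assented, late recruitment was unconcealed, and the protections of 8.5 and 9.5 are written for effectiveness outcomes, not for the safety analyses that 5.2 treats as a separate type. Followed as written, the plan gives a log-rank test that mixes the population fixed before randomisation with one selected after it.

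Under a true HR of 1, selection alone gives about 0.90 to 1.11 for joiners at 0.5 to 0.7 times the hazard and shares of 20% to 30%. Immortal time alone gives about 0.88 to 1.14, and only if time runs from home randomisation without left truncation and shares differ. These are illustrations under assumed inputs; the SAP does not show that either imbalance occurred, or in which direction. Delayed entry removes the second mechanism but not the first.

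**What to change.** In 10.5:

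1. Run the log-rank test, and any Cox model, in residents consented or assented before their home's randomisation, by original allocation, with time from the home's randomisation. This mirrors the cohort rule in 5.2.2(b) and 8.5.
2. Present the analysis of all consenters alongside it, on the same time scale, with late joiners entering the risk set at their consent date (left truncation; the entry option of Stata's stset).
3. Keep the all-resident death-rate comparison, labelled as independent of consent but including residents admitted after randomisation.

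The cost is a few sentences, one software option and fewer deaths in the restricted analysis. As an illustration, take 78 homes split 31:47 at 2:3, with 10.7 residents each (Table 4: 7.5 at follow-up after 30% loss, 7.5/0.7). That is 332 + 503 = 835 residents and 835 × 0.34 = 284 deaths. At an assumed 25% joiner share in both arms, all consenters would give about 335. The standard error of the log HR rises from 0.11 to 1/√(284 × 0.24) = 0.12.
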